## **4. IRB APPROVAL AND FDA AMENDMENTS**

The Investigator will obtain, from the University of Pittsburgh Institutional Review Board (IRB), prospective approval of the clinical protocol and corresponding informed consent form(s);

modifications to the clinical protocol and corresponding informed consent forms, and advertisements (i.e., directed at potential research subjects) for study recruitment.

The only circumstance in which a deviation from the current IRB-approved clinical protocol/consent form(s) may be initiated in the absence of prospective IRB approval is to eliminate an apparent immediate hazard to the research subject(s). In such circumstances, the Investigator will promptly notify the University of Pittsburgh IRB of the deviation. The Investigator should also notify the sponsor of this event.

The University of Pittsburgh IRB operates in compliance with FDA regulations at 21 CFR Parts 50 and 21 CFR 56, and in conformance with applicable International Conference on Harmonization (ICH) Guidelines on Good Clinical Practice (CGP).

In the event that the University of Pittsburgh IRB requires, as a condition of approval, substantial changes to a clinical protocol submitted under an FDA-accepted IND application, or in the event of the Investigator's decision to modify the previously accepted clinical protocol, the Sponsor will submit (i.e., in advance of implementing the change) a Protocol Amendment to the IND describing any change to a Phase 2 or Phase 3 protocol that significantly affects the safety of subjects, the scope of the investigation, or the scientific quality of the study.

## **5. RECRUITMENT AND INFORMED CONSENT PROCEDURES**

### **5.1 RECRUITMENT METHODS**

The following recruitment methods will be used to identify potential subjects. All recruitment procedures and materials must be reviewed and approved by the IRB prior to their use.

- (1) Potential subjects may be recruited from university and the University of Pittsburgh Research Participant Registry (Pitt+Me), and community advertisements including, but not limited to newspapers internet ads, bulletin boards, posters, and flyers.
- (2) Potential subjects for this study may also be recruited from the REDS-III RBC-Omics Study (IRB# 13115; PI: [name]). Subjects who were enrolled in the studies have provided previously their written informed consent to be contacted for future studies. For the REDS-III RBC-Omics Study, the study investigators/coordinators of the REDS-III RBC-Omics study will identify potential subjects from the original REDS-III RBC-Omics Study cohort. They will review eligibility criteria based on previously gathered research data on the subjects and if eligible, reach out via phone\*and/or email to inform the subject. They will provide the subject with the biotin study coordinator phone number. The REDS-III RBC-OMICs subjects who choose to call will be asked to give verbal permission (waiver to document consent) to allow the biotin study team to review their identifiable genetic information. This will be used to determine if subjects are eligible for the biotin study or to serve as the biotin control.
- (3) Potential subjects may also be recruited via our existing contacts with normal healthy volunteers, support groups, and clinics throughout the University of Pittsburgh areas.

- (4) For subjects who are not patients in the physician investigators' UPMC Presbyterian/Montefiore-based clinics, we will obtain a waiver of written HIPAA permission to review their medical records for eligibility.
- (5) Subjects referred from facilities outside the UPMC Epic medical record system will be provided a medical record release for their physician to release needed documents to confirm eligibility.
- (6.) The study team may be using a secure UPMC email system to do pre-screening questions using the biotin screening script. The study team may email the biotin screening script pre-screening questions using a secure UPMC email system to the subject, as soon as the subject fills out the questions, then the subject will email it back to study team. Then the study team will print out a hard copy of subject's responses to the pre-screening questions and then the study team will delete the subject's email. The study team will keep the hard copy of the pre-screening questions in a locked cabinet in a locked office on a unit that has restricted access until the subject comes in for a screening visit. The subject's pre-screening form will be stored for approximately several months and will be destroyed if the subjects do not go to a screening visit and sign consent.

## **5.2 INFORMED CONSENT PROCEDURES**

Prior to performing any of the study procedures the subjects must provide informed consent. The information about this study will be given to potentially eligible subjects in language understandable to them. The physician investigator or the study coordinator will verbally present a general outline of the research study, including potential risks and benefits of participation, to the prospective participant. The consent form, outlining the design of the study and including the risks and benefits of participating, will be reviewed with the prospective participant by the physician investigator who will answer any questions at that time. Prospective participants will have ample time and opportunity to ask questions and will be informed about the right to withdraw from the study at any time without any disadvantage and without having to provide any reasons for this decision. Participants will receive a copy of the informed consent form.

The RBC-OMICs control subjects may be asked to return up to a maximum of 6 times in one year to MUH-CTRC for additional optional blood draw visits. The biotin study team will ask the subjects questions related to the consent to confirm subjects comprehension of the study.

The physician investigator or study coordinator will verbally present from the consent that the individual genetic results or incidental findings will not be shared with subjects as these tests are research-related and these initial finding will need additional research before their clinical significance is understood and appropriate actions are determined.

During the course of the study, participants will be provided with any new information that arises (i.e., new study procedure, change in risk/benefit profile) that may affect a participant's decision whether or not to continue participation in the study. Subjects who already signed consent will be presented with a revised consent form with the new study procedures and/or what has changed since they last provided consent. A copy of the revised consent will be given to the subjects for their records.

## **6. POTENTIAL RISKS AND BENEFITS**

## 6.1 POTENTIAL RISKS

As with any experimental procedure, there may be adverse events or side effects that are currently unknown, and certain of these unknown risks could be permanent, severe or life threatening. Every attempt will be taken to minimize these risks.

Risks of BioRBC Infusion: The risks of BioRBC infusion include the possibility that the biotinylated cells may be destroyed and cleared from the circulation. The amount of transfused BioRBCs represents about 2% of the total blood volume in the subject and removal of the BioRBCs are not likely to cause any health problems. During the biotinylation process, the autologous RBCs will be removed from the blood bank and processed under a sterile tissue culture hood. The biotinylation process will be performed in a GMP cellular therapy facility; however there is a minimal risk of bacterial contamination. This risk is reduced by requiring that each BioRBC sample be tested for and passes endotoxin contamination testing prior to infusion.

Risk of Antibody Formation: In a previous study in which adults were transfused with BioRBCs, 3 of 20 (15%) subjects developed antibodies to BioRBCs, but none developed anemia or any other health problems. In study subjects that developed antibodies, the antibodies disappeared from the blood over a period of months. To reduce this risk of antibody formation, a lower dose of biotin will be used throughout this study compared to the previous study, and subjects will be screened for antibody formation throughout the study and during follow-up visits. In summary, we do not anticipate side effects in the proposed biotin doses.

Rare risks include immune-mediated hemolytic reaction to transfused biotinylated RBCs. Given the small volume of BioRBC infused, no significant clinical effects of hemolysis of biotinylated RBC is expected.

Risks of Transfusion Reactions: In this study, healthy subjects receive only small volume of autologous packed BioRBCs. The risk of experiencing a transfusion reaction is considered minimal; no excess risk of transfusion reactions is expected from the small autologous infusions used in this study. However, adverse reactions that are known to occur following transfusion. Specifically, transfusions of conventional blood products are known to be associated with adverse transfusion reactions such as fever, chills, nausea/vomiting, itching, rash, hives, hemolysis, bronchospasm, hypertension and hypotension, transfusion-related acute lung injury (TRALI), transfusion-associated circulatory overload (TACO), and anaphylaxis.

Risk of Blood Donation: The risks include nausea, fainting or dizziness, low blood pressure, bruise at needle puncture site, possible nerve damage, blood loss and infection. Other less common risks include phlebotomy complications, fainting (vasovagal) reactions, chance of identifying communicable disease and stress, emotional distress on subject. We will follow the AABB's blood drawing guidelines along with the hospital's standard operating procedures for adult venipunctures.

Risks of Venipuncture /Intravenous Needle Insertion: Common Risks: bruising, soreness, phlebitis. Infrequent Risks: infiltration (a leakage of anything that has been given through the vein (such as the saline) into the arm tissue that surrounds the vein and holds the IV), mild pain and discomfort at the injection or needle insertion site as well as possible infection and bleeding. Rare: severe pain; swelling; fainting. In order to minimize the potential for fall injuries, subjects will be closely monitored for dizziness or light-headedness before they are allowed to stand.

### Risks of Collection of Private Health Information, Biospecimens and Genetic Analysis:

Participation in this research study does involve the potential risks of a breach of confidentiality of the medical record information and associated privacy of the participants. This research study will result in identifiable information that will be placed into the subject's medical records held at the University of Pittsburgh Medical Center. The nature of the identifiable information resulting from participation in this research study that will be recorded in the medical record includes laboratory test results. This potential for breach of confidentiality, including with regard to genetic analysis, could impact future insurability, employability, or reproduction plans, or have a negative impact on family relationships, and/or result in paternity suits or stigmatization. If the subject is eligible from visit 1, then Vitalant's form "Physician Order for Autologous Blood" will be sent to Vitalant staff via the UPMC secure email system. This form will have the subject's private health information and the study ID number that is reviewed and signed/dated by the PI or Co-I in this study prior to visit 2. In order for the blood to be released from Vitalant to the HSCLab, Vitalant will need this form. A "Physician's Processing Request form" will be sent to the HSCLab staff via the UPMC secure email system. This form will have the subject's private health information and the study ID number that is reviewed and signed/dated by the PI or Co-I in this study. In order for the blood to be released from HSCLab to CTCR, HSCLab will need this form. The Vitalant form, "Patient Identification Form" that is sent to HSCLab by the study team via the UPMC secure email system will contain the subject's private health information and study ID number. In order for the blood to be released from Vitalant to HSCLab on the day of biotinylation, Vitalant will need this form. The study team will make every effort to keep the subject's medical information and study ID confidential.

## **6.2 ALTERNATIVE TREATMENTS**

If subjects choose not to participate in this study, they are to continue their medical care under the direction of their treating physicians.

## **6.3 POTENTIAL BENEFITS**

There will be no direct benefit to the subjects participating in this study, but the society at large may benefit from the increased knowledge gained from this study. This study will advance the general knowledge regarding the effect of the storage lesion of red cell transfusion on endothelial function, and evaluate the metabolism and interconversion of nitrite to nitric oxide *in vivo* in healthy adults as a means to ameliorate the endothelial effects of the storage lesion, and study the lifespan of transfused red cells. This may have a major impact on how we transfuse red cells in patients.

Based on the preceding assessment of risks and potential benefits, the risks to subjects are reasonable in relation to anticipated benefits. The research presents a balance of risks and expected benefits similar to that available in the clinical setting.

## **6.4 DATA SAFETY MONITORING**

### **6.4.1 Data Safety Monitoring Board**

An Independent Data and Safety Monitoring Board (iDSMB) will be established; to be comprised of individuals who are not involved with this study protocol. The iDSMB will comprise of members including senior experts in transfusion medicine, clinical research and clinical trial design. None

of the DSMB members will have direct involvement in the conduct of the study. All members of the DSMB are required to be independent of the studies being reviewed and need to certify this by signing a DSMB Conflict of Interest and Confidentiality statement.

The iDSMB will conduct interim monitoring of accumulating data from research activities to assure the continue safety of human subjects, relevance and appropriateness of the study, and the integrity of research data.

#### **6.4.2 Data Safety Monitoring Plan**

Before the start of the study, the DSMB will review the protocol for any major concern and the plans for data and safety monitoring to ensure that the frequency of monitoring is appropriate for the intervention. In addition, certification of IRB approval of the protocol with the data and safety monitoring plan will be sent to the NHLBI Grant Program Official (PO) prior to implementation.

Once the study is implemented, the DSMB will convene as often as necessary, but not less than every 6 months, to examine the accumulated safety and enrollment data, review study progress, and discuss other factors (internal or external to the study) that might impact continuation of the study as designed. A DSMB meeting may be requested by DSMB members, the PO, IRB, or study PI at any time to discuss safety concerns. Meetings may be held by conference calls or videoconferences or as face-to-face meetings.

During the study, the DSMB will review cumulative study data to evaluate safety, study conduct, and scientific validity and integrity of the trial as well as to assess the performance of overall study operations and any other relevant issues, as necessary. The DSMB will conclude each review with their recommendations to NHLBI, IRB and other applicable oversight bodies as to whether the study should continue without change, be modified, or terminated.

The study PI will ensure that the DSMB is apprised of all new safety information relevant to the study product and the study, including all protocol revisions, summary safety and enrollment data and all safety reports issued by the IND sponsor.

The IND Sponsor will also submit annually an Annual Report to the FDA. The detailed written summary will be provided to the DSMB and the IRB. In addition, the DSMB Report will be submitted to the IRB at the time of continuing review annually or more often as required.

Monitoring of safety and data quality in the proposed study will be the responsibility of all personnel on the project, with primary responsibility and supervision by the Investigator. The Institutional Review Board will approve the Statement of Informed Consent for the study and provide institutional oversight of data and safety issues. The study protocol will be approved prior to recruiting or obtaining consent from any participants. Moreover, the study will be reviewed at a minimum of annual basis (or more frequently as deemed necessary) by the IRB committee. Each participant will sign the Informed Consent Form described above prior to participating in the study. To ensure participant safety, once participants are enrolled in the study, study staff will immediately report all adverse and serious adverse events to one of the Investigators. The Investigator will, per standardized procedures, report them to the IRB for their review. These events should also be communicated to the sponsor of the IND. With regard to monitoring of data quality and protected health information, all required personnel proposed for this project will have the required human subjects and confidentiality training, which includes information about maintaining data integrity and security. Confidentiality will be guarded using established procedures such as storing data in locked cabinets within locked offices or locked data rooms,

coding by study identification numbers rather than any personally identifying information to avoid revealing the identity of subjects, and aggregating data across participants. The key linking names and study identification numbers will be kept separately from the data sets with limited access by study personnel. However, Vitalant staff members and the HSCLab staff members will need to have the study ID number on documents with the subjects name to add to the level of protection when identifying the subject's blood unit and in order for the blood to be released. Only study personnel will have access to the data sets on protected servers. Oversight of all aspects of data management will occur with the Investigator. Subject's de-identified biological samples and data will be stored for future research analyses and may be shared with other researchers', their laboratories or federal repositories.

Only the REDS-III RBC-OMICS subject's de-identified biological samples and data may contain the subject's SNP and will be stored for future research analyses and may be shared with other researchers', their laboratories or federal repositories. The subject's de-identified biological samples and data may contain the subject's SNP for the biotin study team to know which SNP subgroup the subject is in. Three of the analyses that may be done at Wake Forest University, Yale University, and Vitalant.

The future analysis could include genetic analyses, including whole genome sequencing.

Data Monitoring Plan. The proposed study will use the FDA definition of adverse events (AE) and serious adverse events (SAE). Any SAE, which is unexpected and related to study intervention, will be reported immediately to the IRB and will be followed by an additional letter detailing the nature of the SAE. In the event that a participant either withdraws from the study or the investigators decide to discontinue a participant due to a SAE, the participant will be monitored by the co-PIs until (a) a resolution is reached (e.g., the problem has resolved or stabilized with no further change expected), (b) the SAE is determined to be clearly unrelated to the study intervention, or (c) the SAE results in death. Outcomes of SAEs will be regularly reported to the IRB and the sponsor. A summary of the SAEs that occurred during the previous year will be included in the annual progress report as well as in the annual IRB renewal.

#### **6.4.3 Parameters to be monitored**

The following progress will be monitored throughout the course of the research to ensure the safety of subjects as well as the integrity and confidentiality of their data.

- An evaluation of the progress of the research study, including subject recruitment and retention, and an assessment of the timeliness and quality of the data.
- A review of collected data (including adverse events, unanticipated problems, and subject withdrawals) to determine whether there is a change to the anticipated benefit-to-risk assessment of study participation and whether the study should continue as originally designed, should be changed, or should be terminated.
- An assessment of external factors or relevant information (eg. pertinent scientific literature reports or therapeutic development, results of related studies) that may have an impact on the safety and study participants or the ethics of the research study.
- A review of study procedures designed to protect the privacy of the research subjects and the confidentiality of their research data.

The severity of adverse changes in physical signs or symptoms will be classified as follows:

- Grade 1 (Mild): asymptomatic or mild symptoms; clinical or diagnostic observation only; intervention not indicated.
- Grade 2 (Moderate): minimal, local or noninvasive intervention indicated; limiting age-appropriate ADL (Activities of Daily Living).
- Grade 3 (Severe): medically significant but not immediately life-threatening; hospitalization or prolongation of hospitalization indicated; disabling; limiting self care ADL.
- Grade 4 (Life-threatening): consequences; urgent intervention indicated.
- Grade 5 (Death): event is a direct cause of death.

#### **6.4.4 Frequency of Monitoring**

The Investigator will review subject safety data as it is generated. The Investigator, sub-investigators, and the research staff will meet on an approximately monthly interval to re-evaluate study goals, subject recruitment, data coding and retention, documentation and identification of adverse events, complaints and confidentiality of subjects. There will be an evaluation of the progress of the research study, including assessments of data quality, time lines, participant recruitment, accrual, and retention. The Investigator will also review the outcome and adverse event data to determine whether there is any change to the anticipated benefit-to-risk ratio of study participation and whether the study should continue as originally designed or should it be re-evaluated and changed.

The DSMB will also be expected to meet as needed, but not less than every six months to provide an overall summary status report to the regulatory agencies.

#### **6.4.5 Reportable Adverse Events**

For this study, a serious adverse event is any untoward clinical event that is thought by either the investigator or the sponsor to be related to the study and results in any of the following outcomes: that is also:

- 1) Death
- 2) A life threatening adverse event
- 3) Inpatient hospitalization or prolongation of an existing hospitalization
- 4) A persistent or significant incapacity or substantial disruption of the ability to conduct normal life functions
- 5) A congenital anomaly or birth defect
- 6) Important medical events that may not result in death, be life threatening, or require
- 7) hospitalization may be considered serious when, based upon appropriate medical judgment, they may jeopardize the patient, or subject, and may require medical, or surgical intervention to prevent one of the serious outcomes listed above.

If clinically important and unexpected adverse experiences or clinically important study-related adverse experiences occur, they will be recorded on the adverse event case report form.

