#### **6.4.8. Withdrawal of Subjects and Stopping Criteria:**

##### **STOPPING RULES:**

**Withdrawal of Subjects:** Subjects must be withdrawn from the study for the following reasons:

- An SAE or a serious post-infusion hemolytic event that is determined to be possibly, probably, or definitely related to the infusion of autologous BioRBC.
- Detection of anti-BioRBC antibodies following first infusion. In the unlikely event that a study subject tests positive for bioRBCs following first infusion, the subject will be withdrawn from

the study. The subject will not receive the subsequent RBC infusion. Since anti-BioRBC antibodies attack BioRBCs, the 2-4 hours post transfusion survival and mean lifespan measurements will be affected. Based on the time of discovery, the 2-4 hours time point measurement may be retained or discarded. The participant will be followed for signs and symptoms of hemolysis as well as the disappearance of the anti-biotinylated RBC antibodies.

Subjects may be withdrawn from the study for the following reasons:

- In the unlikely event that a stored unit does not pass the endotoxemia test, red blood cells will not be transfused and will have to be withdrawn from the study.
- In the event that a donated RBC unit is misplaced, the subject's participation in the study will be terminated since an autologous transfusion will no longer be possible.
- At their own request
- At the specific request of the Investigator (eg detection of a new significant safety concern related to the study drug).
- Occurrence of intercurrent diseases which in investigator's opinion, continuation of the study drug would be harmful to the subject's well-being.
- Pertinent non-compliance with the conditions for the trial or instructions by the investigator.
- Lost to follow up

Any subject removed from the study will remain under medical supervision until the condition is medically acceptable. Study subjects removed from the study will be replaced by enrolling another volunteer with similar demographic

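### The SAE definition in section 6.4.5 requires relatedness, which conflicts with section 6.4.2 and leaves serious events judged unrelated out of the SAE counts

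*Combined protocol and SAP*

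**What the plan says.** Section 6.4.5 (Reportable Adverse Events) sets two conditions for an SAE. The event must be one that "is thought by either the investigator or the sponsor to be related to the study", and it must lead to one of the listed outcomes, such as death, a threat to life, or hospitalization. The section then gives the rule for the adverse event form. Entry is required "If clinically important and unexpected adverse experiences or clinically important study-related adverse experiences occur".

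Section 6.4.2 (Data Safety Monitoring Plan) uses the term differently. Under its data monitoring paragraph, "Any SAE, which is unexpected and related to study intervention, will be reported immediately to the IRB". A subject who leaves the study because of an SAE is monitored until one of three end points, and one of these is that "the SAE is determined to be clearly unrelated to the study intervention". SAE outcomes go regularly to the IRB and the sponsor, and a yearly SAE summary goes into the progress report and the IRB renewal. The same section also has a general reporting route: "study staff will immediately report all adverse and serious adverse events to one of the Investigators", after which the Investigator reports them to the IRB, and they should also be communicated to the IND sponsor.

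Section 6.4.8 requires withdrawal for an SAE or serious hemolytic event "determined to be possibly, probably, or definitely related to the infusion of autologous BioRBC".

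**The concern.** Seriousness describes what happened to the subject. Relatedness is a judgement about why it happened. When the second is part of the definition of the first, the causality judgement decides whether the event is counted at all. An SAE summary built on that definition cannot show how many serious events were set aside as unrelated, so a reader of the summary has nothing to check the judgement against.

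Staff also cannot tell which usage governs. Section 6.4.5 implies that every SAE is already thought related. Section 6.4.2 implies that an SAE can be unrelated, and that related SAEs are a subset. At stake are the completeness of the SAE count and, for one class of event, whether it is entered on the form.

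**Working it through.** No formula applies, and the plan states no figure to reproduce. The check compares the rules and then follows a serious event through each of them.

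**Step 1: compare the uses of the term.**
- 6.4.5, definition: an SAE must be thought related to the study by the investigator or the sponsor.
- 6.4.2, end of follow-up: an SAE may be found clearly unrelated to the study intervention. This is hard to reconcile with 6.4.5, where an event that neither party thinks related was never an SAE.
- 6.4.2, immediate IRB reporting: applies to SAEs that are unexpected and related. If every SAE is already thought related, the second qualifier does little work.
- 6.4.8, withdrawal: asks whether the event is related to the BioRBC infusion. This is narrower than being related to the study, so it is consistent with 6.4.5 and is not part of the conflict.

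**Step 2: follow a serious event through the rules.** Take an event with one of the listed outcomes, and assume that it counts as clinically important for the form rule.

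| Judgement | SAE under 6.4.5? | In the 6.4.2 SAE summary and outcome reports? | On the AE form under 6.4.5? | Sent to Investigator, IRB and IND sponsor under 6.4.2? |
|---|---|---|---|---|
| Thought related by either party, unexpected | Yes | Yes | Yes | Yes |
| Thought related by either party, expected | Yes | Yes | Yes (related branch) | Yes |
| Thought related by neither, unexpected | No | No | Yes (unexpected branch) | Yes, as an adverse event |
| Thought related by neither, expected | No | No | Not covered by either branch | Yes, as an adverse event |

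**Step 3: read the result.** Both rows in which neither party sees a relation lose the SAE label and fall out of the SAE outputs. Only the last row also falls outside the form rule. For example, section 6.1 lists fainting as a known risk of donation and needle insertion. A hospitalization for fainting some weeks after a visit, judged expected and unrelated, would be neither an SAE nor a required form entry, but it would still go to the IRB and the IND sponsor as an adverse event.

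**The case against.** The strongest reply is that little is lost. Section 6.4.2 has every adverse event reported with no causality filter, 6.4.3 and 6.4.4 review adverse events in general, and Appendix A schedules an AE assessment at infusion visits V3 to V10. This stands. A reader might infer that unrelated serious events vanish from the safety data. The documents do not support that; the loss is from the SAE category and, in one row of the table, from the form rule.

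The two sections can also be partly harmonized. An event caused by the blood donation is related to the study but not to the infusion, so it could be an SAE that is unrelated to the intervention. A first impression of relatedness could also be overturned later. Both readings soften the conflict, but the plan states neither. Neither brings back an event that no one thought related to any part of the study.

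Four further inferences are tempting and do not hold:
- That the iDSMB sees only a filtered list. Section 6.4.2 gives it accumulated safety data and new safety information, and does not limit it to events labelled as SAEs.
- That adverse event rates across genetic groups become incomparable. Sections 2.4 and 2.5.2 plan no between-group safety comparison, and one definition applies to every group.
- That the withdrawal rule in 6.4.8 is incoherent. Its qualifier concerns the infusion and is meaningful as written.
- That 6.4.5 breaches the FDA definition that 6.4.2 says the study will use. The documents name that definition but do not reproduce it, so the point rests on the conflict between 6.4.5 and 6.4.2.

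The form gap is probably small as well. The subjects are healthy volunteers with wide exclusions in 3.3, and few serious events are likely to be both expected and unrelated.

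**Conclusion.** The point holds in a limited form. The definition in 6.4.5 conflicts with the use of the term in 6.4.2. Followed as written, it removes from the SAE summary and outcome reports every serious event that both the investigator and the sponsor judge unrelated. Those that are also judged expected fall outside the form rule. All of them still reach an Investigator, the IRB and the IND sponsor as adverse events. No efficacy endpoint or planned analysis depends on this.

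The size cannot be given as a count, because the documents state no serious event rate. As an illustration only, assume that 2% to 5% of the roughly 90 subjects expected to complete the infusion study (section 2.5.1) have a serious event of any cause. That is 0.02 × 90 = 1.8 to 0.05 × 90 = 4.5 events. This is a ceiling, since only events that both parties judge unrelated are affected. The assumed rate has no support in the documents, and the conclusion does not rest on it.

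The conclusion assumes that 6.4.5 is applied literally, that serious events count as clinically important for the form rule, and that no separate procedure outside these documents already records all serious events.

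**What to change.** Reconcile 6.4.5 with 6.4.2 as follows:
- Delete the relatedness clause from the SAE definition in 6.4.5, so that an SAE is defined by its outcome alone.
- Require every serious event to be entered on the case report form, whatever its cause or expectedness.
- Record relatedness and expectedness as separate fields on that form.

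The expedited reporting text in 6.4.6 and the withdrawal text in 6.4.8 carry their own qualifiers and stay as they are. This takes the infusion qualifier in 6.4.8 to cover SAEs as well as hemolytic events. The annual SAE summary and outcome reports in 6.4.2 need no new wording; they would simply include unrelated events, marked as such.

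The cost is a wording amendment and slightly more form entry. Sample size, visits and analyses do not change.
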